9.1 Adverse Event Collection in the Case Report Forms

All adverse events that occur beginning with start of treatment (minus exceptions defined in Section 8.0) must be captured in the Toxicity Form. Baseline AEs should be captured on the Medical History Form.

Participant death due to disease progression should be reported on the Toxicity Form as grade 5 disease progression. If death is due to an AE (e.g. cardiac disorders: cardiac arrest), report as a grade 5 event under that AE. Participant death must also be recorded on the Death Form.

10.0 MEASUREMENT OF EFFECT

10.1 IWG-MRT Response Criteria

Objective response is defined as CR (complete remission/response) + PR (partial remission/response) + CI (clinical improvement). Responses are defined by the International Working Group-Myeloproliferative Neoplasms Research and Treatment (IWG-MRT) consensus [59]:

Complete Response (CR):

- Bone marrow: Age-adjusted normocellularity; <5% blasts; \leq grade 1 MF
AND
- Peripheral blood: Hemoglobin \geq 10 g/dL; neutrophil count \geq $1 \times 10^9/L$; platelet count $\geq 100 \times 10^9/L$ and < UNL; <2% immature myeloid cells
AND
- Clinical: Resolution of disease symptoms; spleen and liver not palpable; no evidence of extramedullary hematopoiesis (EMH)

Partial Response (PR):

- Peripheral blood: Hemoglobin \geq 10 g/dL; neutrophil count $\geq 1 \times 10^9/L$; platelet count $\geq 100 \times 10^9/L$ and < UNL; <2% immature myeloid cells
AND
- Clinical: Resolution of disease symptoms; spleen and liver not palpable; no evidence of extramedullary hematopoiesis (EMH)
OR
- Bone marrow: Age-adjusted normocellularity; <5% blasts; \leq grade 1 MF
AND
- Peripheral blood: Hemoglobin ≥ 8.5 but < 10 g/dL and < UNL; neutrophil count $\geq 1 \times 10^9/L$ and < UNL; platelet count $\geq 50 \times 10^9/L$, but < $100 \times 10^9/L$ and < UNL; <2% immature myeloid cells
AND
- Clinical: Resolution of disease symptoms; spleen and liver not palpable; no evidence of EMH

Clinical Improvement (CI):

- The achievement of anemia (10.2.1), spleen (10.4) or symptoms response (10.3) without progressive disease or increase in severity of anemia, thrombocytopenia, or neutropenia

Stable Disease (SD):

- Not meeting the definition of CR, PR, CI or PD

Progressive Disease (PD):

- Appearance of a new splenomegaly that is palpable at least 5 cm below the LCM
OR
- A $\geq 100\%$ increase in palpable distance, below LCM, for baseline splenomegaly of 5-10 cm
OR
- A $\geq 50\%$ increase in palpable distance, below LCM, for baseline splenomegaly of > 10 cm
OR
- Leukemic transformation confirmed by a bone marrow blast count of $\geq 20\%$
OR
- A peripheral blood blast content of $\geq 20\%$ with an absolute blast count of $\geq 1 \times 10^9/L$ for at least 2 weeks

10.2 Hematologic Response

10.2.1 Anemia Response

Anemia response is only applicable for patients with a baseline hemoglobin level less than 10 g/dL for 8 weeks or more, and requires:

- ≥ 2 g/dL increase in hemoglobin level
OR
- becoming transfusion-independent (no RBC transfusions in past 1 month)

10.2.2 Platelet Response

Platelet response is only applicable for patients with a baseline platelet count of less than $50 \times 10^9/L$ for 8 weeks or more, and requires:

- An absolute platelet count of at least $50 \times 10^9/L$ on two separate measurements at least 2 weeks apart

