	APPENDIX C: PATIENT'S MEDICATION DIARY	49
	APPENDIX D: Definitions for Adverse Event Reporting	50
	APPENDIX E: Reporting Timelines	53
	APPENDIX F: Symptom Assessment Form	56

PROTOCOL SUMMARY

Synopsis

Title:	Fostamatinib as a single agent or in combination with ruxolitinib for treatment of patients with myelofibrosis with severe thrombocytopenia
Study Description:	
Our hypothesis is that fostamatinib will be safe, tolerable, and effective in patients with myelofibrosis with severe thrombocytopenia (platelet < 50K/microL) as a single agent and in combination with ruxolitinib. Fostamatinib will improve thrombocytopenia in patients with myelofibrosis (MF) with severe thrombocytopenia (platelet < 50K/microL) and allow them to initiate treatment with ruxolitinib.
 
This study will be executed in two parts (Part A and Part B). For Part A, patients with MF with severe thrombocytopenia will initially receive 12 weeks of single agent fostamatinib (by mouth twice daily) until a sustained platelet count of ≥ 50K/microL is achieved (defined as two separate measurements at least two weeks apart).
 
Patients who achieve a sustained platelet count of ≥ 50K/microL will be eligible to continue on to Part B where they will begin treatment with ruxolitinib (dosed as per standard of care) while continuing to take fostamatinib. Patients who do not achieve a sustained platelet count of ≥ 50K/microL by the end of 12 weeks of treatment may continue on fostamatinib monotherapy if they are receiving benefit for up to an additional 36 weeks of treatment, and may be eligible to continue on to Part B of the study if they achieve a sustained platelet count of ≥ 50K/microL at any point before Cycle 10 Day 1.
 
Patients in Part B will continue treatment with fostamatinib and ruxolitinib for up to an additional 36 weeks (total duration of treatment with fostamatinib monotherapy and fostamatinib and ruxolitinib combination therapy will be 48 weeks).

Objectives:	
Part A:
 
Primary Objective: Evaluate the impact of fostamatinib on platelet counts in patients with myelofibrosis and severe thrombocytopenia (platelets < 50K/microL)
 
Secondary Objectives:
 
 Evaluate the safety and tolerability of single agent fostamatinib in patients with MF and thrombocytopenia Evaluate spleen response to fostamatinib

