	
 3. Evaluate anemia response to fostamatinib 4. Evaluate the impact of fostamatinib on transfusion requirements 5. Evaluate the impact of fostamatinib on MF symptoms 6. Evaluate the ability of fostamatinib treatment to enable initiation with ruxolitinib 7. Evaluate the impact of fostamatinib on marrow fibrosis 
Part B:
 
Primary Objective: Evaluate the safety and tolerability of fostamatinib plus ruxolitinib in patients with MF and thrombocytopenia
 
Secondary Objectives:
 
 1. Evaluate spleen response with the combination of fostamatinib and ruxolitinib 2. Evaluate the impact of fostamatinib and ruxolitinib on symptoms 3. Evaluate the ability of fostamatinib to enable sustained treatment with ruxolitinib 4. Evaluate the impact of fostamatinib and ruxolitinib on marrow fibrosis
Endpoints:	
Part A:
 
Primary Endpoint: Platelet response as defined as an increase in platelet count $\geq 50K/\text{microL}$ with at least one more confirmatory platelet count separated by at least 2 weeks (in the absence of platelet transfusion) within the first 12 weeks of fostamatinib treatment
 
Secondary Endpoints:
 
 1. Platelet response by week 12 and at end of fostamatinib monotherapy treatment 2. Number of patients eligible to initiate therapy with ruxolitinib 3. Adverse events (AEs), serious AEs (SAEs), and laboratory abnormalities on fostamatinib treatment 4. Patients who permanently discontinued fostamatinib due to fostamatinib related AEs 5. Patients who required treatment interruption of fostamatinib due to AEs 6. Patients who were dose escalated who tolerated fostamatinib dose greater than 100 mg BID 7. Patients who achieve 35% or greater reduction in spleen volume as determined by ultrasound at week 12 of fostamatinib treatment and end of fostamatinib monotherapy treatment

	
 8. Mean reduction in spleen volume as determined by ultrasound at week 12 of fostamatinib treatment and end of fostamatinib monotherapy treatment 9. Patients with 50% or greater improvement in Total Symptom Score at week 12 of treatment and end of fostamatinib monotherapy treatment 10. Patients who achieve platelet transfusion independence 11. Patients with anemia who achieve RBC transfusion independence 12. Change in marrow fibrosis by WHO grading

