2.0 OBJECTIVES AND ENDPOINTS

2.1 Part A Objectives and Endpoints

Objectives	Endpoints	Justification for Endpoints
Primary		
To evaluate the impact of fostamatinib on platelet counts in patients with myelofibrosis and severe thrombocytopenia	Platelet response as detailed in Section 11.2.2, platelet response by week 12 and end of fostamatinib monotherapy treatment, and number of patients eligible to initiate treatment with a JAK2 inhibitor (ruxolitinib)	The efficacy of fostamatinib on thrombocytopenia in MF patients is unknown
Secondary		
To evaluate the safety and tolerability of single agent fostamatinib in patients with MF and thrombocytopenia	Incidence, severity, frequency, and outcomes of AEs and SAEs as defined by CTCAE v5.0 criteria, AEIs, laboratory abnormalities, and number of patients who permanently discontinue fostamatinib due to fostamatinib-related AEs, number of patients who require treatment interruptions due to fostamatinib-related AEs	The safety and tolerability of fostamatinib in MF patients is unknown.
To evaluate spleen response in patients with MF receiving fostamatinib	Spleen response as detailed in Section 11.4 at week 12 and end of fostamatinib monotherapy treatment, mean reduction in spleen volume as determined by ultrasound at week 12 and end of fostamatinib monotherapy treatment	The efficacy of fostamatinib on reducing spleen size in MF patients is unknown
To evaluate anemia response in patients with MF receiving fostamatinib	Anemia response as detailed in Section 11.2.1	The impact of fostamatinib on anemia in MF patients is unknown

To evaluate the impact of fostamatinib on constitutional symptoms in patients with MF	Constitutional symptoms as detailed in Section 11.3 at week 12 and end of fostamatinib monotherapy treatment	The efficacy of fostamatinib on improving symptoms in MF patients is unknown
To evaluate the impact of fostamatinib on transfusion requirements	Number of patients who achieve platelet and RBC transfusion independence who were previously requiring transfusions	The impact of fostamatinib on transfusion burden in MF patients is unknown
To evaluate the impact of fostamatinib on marrow fibrosis	Change in marrow fibrosis per WHO grading on bone marrow biopsy performed at the end of fostamatinib monotherapy	The impact of fostamatinib on marrow fibrosis is unknown

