12.2 Study Design

This is a hypothesis generating limited pilot phase II study evaluating the efficacy and safety of the use of fostamatinib as a single agent and when given in combination with ruxolitinib in patients with intermediate to high risk myelofibrosis. Previous studies with fostamatinib and ruxolitinib monotherapy indicate that toxicity will be low grade and reversible with standard treatment.

This study consists of two parts. For Part A, patients with MF and severe thrombocytopenia will initially receive 12 weeks of single agent fostamatinib and the primary endpoint will be platelet response (defined as platelet count of $\geq 50K/\text{microL}$ as two separate measurements at least two weeks apart) at the end of the 12 week treatment period. Patients who achieve a sustained platelet response will then be eligible to proceed to Part B of the study and begin treatment with ruxolitinib while continuing to take fostamatinib. For Part B, patients will continue treatment with fostamatinib and ruxolitinib for up to an additional 36 weeks and the primary endpoint will be safety as assessed by NCI CTCAE v 5.0. Patients who do not have a sustained platelet response after 12 weeks of treatment but are clinically benefiting from fostamatinib may remain on Part A of the study and be eligible to enroll in Part B if they achieve a sustained platelet response prior to Day 1 Cycle 10 of treatment.

A maximum of 12 patients will be enrolled. A Bayesian sequential monitoring rule will be implemented for safety.

Safety monitoring (Part B): The stopping rule is defined as $\text{Pr}(\theta > \theta_T | \text{data}) > 0.8$, where θ denotes the proportion of AEs of interest as defined in Section 5.5 and θ_T denotes the rate of AEs of interest under the null hypotheses (i.e., 20% AEs of interest). That is, an early termination of the study due to excessive toxicities will be recommended whenever, given the accumulated observed data, there is high chance (i.e., >80% probability) for the “true” AEs of interest rate >20%. The stopping boundaries were obtained using Multc99 version 2.1, a free-download software from M.D. Anderson Cancer Center. Specifically, we assume that the parameter θ follows a prior distribution of beta (0.2, 0.8), i.e., θ with mean = 0.2 but with relatively large variability (non-informative prior). Early stopping will be recommended if we observe 3 patients who experience AEs of interest out of first 5 patients

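### The Part A primary endpoint, platelet response, is defined inconsistently: only the synopsis excludes transfusion-supported counts, section 2.1 makes primary two items the synopsis lists as secondary, and threshold and timing wording differ

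*Combined protocol and SAP*

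**What the plan says.** The Part A primary endpoint is described in four places.

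- **Synopsis, Endpoints.** The primary endpoint is worded as an increase in platelet count, followed by the 50K/microL figure, "with at least one more confirmatory platelet count separated by at least 2 weeks (in the absence of platelet transfusion) within the first 12 weeks", counted from the start of fostamatinib. The first two secondary endpoints are: "Platelet response by week 12 and at end of fostamatinib monotherapy treatment 2. Number of patients eligible to initiate therapy with ruxolitinib".
- **Section 2.1, primary row.** "Platelet response as detailed in Section 11.2.2, platelet response by week 12 and end of fostamatinib monotherapy treatment, and number of patients eligible". The eligibility meant is for ruxolitinib. There is no section 11.2.2; platelet response is defined in 10.2.2.
- **Section 10.2.2.** For patients whose baseline count was below 50 x 10^9/L for 8 weeks or more, response is an absolute count of at least 50 x 10^9/L "on two separate measurements at least 2 weeks apart". Transfusion is not mentioned.
- **Section 12.2.** For Part A, "the primary endpoint will be platelet response", defined by a count of at least 50K/microL "as two separate measurements at least two weeks apart) at the end of the 12 week treatment period". Transfusion is not mentioned here either.

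Section 5.7 allows platelet transfusion at the treating physician's discretion. Section 12.3 makes all analyses descriptive, with exact 95% confidence intervals for response rates. Section 12.4 sets the sample at 12 patients without a formal power calculation.

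**The concern.** In a 12-patient study with no comparison and no test, the platelet response rate is the main efficacy result, so its definition carries the weight. The analyst's natural route is from the 2.1 primary row to the measurement section, and that route ends at the version without a transfusion condition. Two counts at or above the threshold that reflect transfused platelets would then be recorded as an effect of fostamatinib. The protocol expects some patients to need platelet transfusions, since becoming independent of them is a secondary endpoint.

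The hierarchy conflict is a separate matter. If 2.1 is followed, the primary result includes outcomes reached well after week 12, because monotherapy may run to 12 cycles. If the synopsis is followed, it does not.

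**Working it through.** **1. The plan's own figures.** Inputs are n = 12 and true rates of 20% and 40% (section 12.4), using the exact binomial.

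- P(X <= 1 | 12, 0.20) = 0.8^12 + 12 x 0.2 x 0.8^11 = 0.275; stated 27%.
- P(X >= 2 | 12, 0.40) = 0.980; stated 98%.

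Both reproduce. They hold for whichever single definition is adopted, so no stated figure has to change.

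**2. The definitions side by side.**

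| Element | Synopsis | 10.2.2 | 12.2 |
|---|---|---|---|
| Threshold | increase, with the 50K figure | absolute count of at least 50 x 10^9/L | count of at least 50K |
| Confirmation | 2 weeks or more apart | 2 weeks or more apart | 2 weeks or more apart |
| Platelet transfusion | excluded | not mentioned | not mentioned |
| Timing | within the first 12 weeks | none (general criterion) | end of the 12-week period |

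**3. Patients whom the texts could classify differently.**

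- *Both counts reach 50K with platelet transfusion support, within 12 weeks.* Responder under 10.2.2 and 12.2; not under the synopsis.
- *Count rises from below 50K to just above 50K.* Responder under 10.2.2 and 12.2. Under the synopsis, responder if its wording means a rise **to** 50K. If it means a rise **of** 50K, a patient with baseline b needs b + 50. Baseline is below 50 by eligibility, so that threshold lies anywhere from 50 to just under 100.
- *Response first confirmed after week 12 on continued monotherapy.* Outside the primary endpoint of the synopsis and 12.2. It can contribute to the 2.1 primary row through end-of-monotherapy response and ruxolitinib eligibility.

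**4. What the hierarchy choice changes.** The Schedule of Activities gives counts on Days 1 and 15 of each cycle, plus Days 8 and 22 of the first. Post-baseline counts up to Cycle 4 Day 1 fall on days 8, 15, 22, 29, 43, 57, 71 and 85, which is 8. Twelve cycles of monotherapy add 17 more, the last on day 323, for 8 + 17 = 25. Extending the period therefore gives about three times as many scheduled counts.

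**5. Effect of one reclassified patient.** The rate moves by 1/12 = 8.3 points. Clopper-Pearson limits are Beta(0.025; x, n - x + 1) and Beta(0.975; x + 1, n - x).

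- x = 2: 2/12 = 16.7%, interval 2.1% to 48.4%.
- x = 3: 3/12 = 25.0%, interval 5.5% to 57.2%.

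The choice of 2 and 3 responders is illustrative.

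**The case against.** The strongest reply is that the synopsis and 12.2 agree on platelet response as the primary endpoint, that analyses are descriptive, and that no decision or error rate depends on the label. That stands, and it limits the consequence. It does not supply the transfusion condition where 10.2.2 and 12.2 lack it, or reconcile 2.1 with the synopsis.

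A reader might infer three stronger criticisms. The documents do not support them.

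- *That 10.2.2 is wrong to have no 12-week window.* Section 10 holds general response criteria; anemia, symptom and spleen response have no assessment time point there either. Timing is set where endpoints are stated. The same definition also serves end-of-monotherapy response, which a 12-week limit in 10.2.2 would disable.
- *That 12.2 calls for a single week-12 readout.* Its sentence requires two measurements at least two weeks apart, so one count at week 12 could not satisfy it. The phrase is loose beside the synopsis but can be read consistently with it.
- *That the denominator is open to choice after the data are seen.* Section 5.6 prespecifies evaluability: a patient is excluded only by stopping before completing Cycle 1 and also having no disease assessment. Weekly counts in Cycle 1 would leave few such patients, if a blood count qualifies as an assessment. The 12 patients in 12.4 are a planning illustration. What remains is a small mismatch: 10.2.2 asks for a low baseline for 8 weeks or more, whereas inclusion criterion 2 asks for at least two low measurements over an 8-week period.

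It is also fair to say that 12.3 covers platelet response under hematologic response rate, the heading of section 10.2.

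**Conclusion.** The point holds and should be fixed. The primary endpoint carries a transfusion exclusion in one place and none in two others, while platelet transfusion is allowed on study. This is a conflict of rules, not merely missing detail. The 2.1 primary row conflicts with the synopsis on two items, and 12.2 sides with the synopsis. The threshold and timing differences are lesser, but they belong in the same correction.

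The size is 8.3 percentage points per reclassified patient, assuming a denominator of 12. The intervals in the example overlap widely. Nothing in the documents shows that any patient would be reclassified. With no test and no success threshold, there is no effect on type I error or power.

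**What to change.** 1. **Section 10.2.2:** keep the absolute threshold and the two-measurement rule. Add that neither count is supported by platelet transfusion, with the transfusion-free interval set by the sponsor. Do not add a 12-week window here.
2. **Synopsis and 12.2:** state the primary endpoint as platelet response per 10.2.2 achieved within the first 12 weeks. This replaces the synopsis's increase wording and the end-of-period phrase in 12.2.
3. **Section 2.1:** move end-of-monotherapy response and ruxolitinib eligibility to secondary, and correct 11.2.2 to 10.2.2.
4. **Synopsis secondary endpoint 1:** remove the week-12 part, or say how it differs from the primary.
5. **Minor:** align the 10.2.2 baseline condition with inclusion criterion 2, so that every enrolled patient evaluable under 5.6 is in the denominator.

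The wording for entry to Part B needs attention at the same time. Section 12.2 uses the endpoint term: "Patients who achieve a sustained platelet response will then be eligible to proceed to Part B of the study". The synopsis description uses a sustained count that "is achieved (defined as two separate measurements at least two weeks apart", and section 5.3 is similar; neither mentions transfusion. Changing 10.2.2 could therefore alter how the 12.2 gate is read. The sponsor should reconcile these passages; no clinical criterion is proposed here.

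The cost is a text amendment with its IRB review, and a sponsor decision on the transfusion-free interval. No new data are needed: the scheduled blood counts and the continuously completed Transfusion Form (section 9.0) suffice. The downside is that the reported response rate may be slightly lower.

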10.3 Symptoms Response

$A \geq 50\%$ reduction in the myeloproliferative neoplasm symptom assessment total symptom score (see Appendix F)

10.4 Spleen Response

- A baseline splenomegaly that is palpable at 5-10 cm below the left costal margin becomes not palpable
OR
- A baseline splenomegaly that is palpable > 10 cm below the left costal margin decreases by $\geq 50\%$
OR
- A baseline splenomegaly that is palpable < 5 cm below the left costal margin is not eligible for spleen response
OR
- Ultrasound shows $\geq 35\%$ spleen volume reduction (calculated)

11.0 DATA AND SAFETY MONITORING

In compliance with the Washington University Institutional Data and Safety Monitoring Plan, the Principal Investigator will provide a Data and Safety Monitoring (DSM) report to the Washington University Quality Assurance and Safety Monitoring Committee (QASMC) semi-annually beginning six months after accrual has opened (if at least five patients have been enrolled) or one year after accrual has opened (if fewer than five patients have been enrolled at the six-month mark).

The Principal Investigator will review all patient data at least every six months, and provide a semi-annual report to the QASMC. This report will include:

- HRPO protocol number, protocol title, Principal Investigator name, data coordinator name, regulatory coordinator name, and statistician
- Date of initial HRPO approval, date of most recent consent HRPO approval/revision, date of HRPO expiration, date of most recent QA audit, study status, and phase of study
- History of study including summary of substantive amendments; summary of accrual suspensions including start/stop dates and reason; and summary of protocol exceptions, error, or breach of confidentiality including start/stop dates and reason
- Study-wide target accrual and study-wide actual accrual
- Protocol activation date
- Average rate of accrual observed in year 1, year 2, and subsequent years
- Expected accrual end date
- Objectives of protocol with supporting data and list the number of participants who have met each objective
- Measures of efficacy
- Early stopping rules with supporting data and list the number of participants who have met the early stopping rules
- Summary of toxicities
- Abstract submissions/publications
- Summary of any recent literature that may affect the safety or ethics of the study

The study principal investigator and Research Patient Coordinator will monitor for serious toxicities on an ongoing basis. Once the principal investigator or Research Patient Coordinator becomes aware of an adverse event, the AE will be reported to the HRPO and QASMC according to institutional guidelines.

